1. SYNOPSIS

Protocol Title:	A Randomized, Double-Blind, Placebo-Controlled, Parallel-Group Study to Evaluate the Efficacy and Safety of Intravenously Administered BIIB092 in Participants with Progressive Supranuclear Palsy
Protocol Number:	251PP301
Version Number:	7
Name of Study Treatment:	BIIB092
Study Phase:	2b
Study Indication:	Progressive Supranuclear Palsy
Study Rationale:	
The neuropathological hallmark of Progressive Supranuclear Palsy (PSP) is the presence of tau pathology in characteristic subcortical and cortical brain regions. N-terminal tau is implicated in mediating the transcellular spreading of this tau pathology in PSP.
 
Based on the available preclinical and clinical data, BIIB092 (formerly known as BMS-986168 and IPN007) is expected to prevent spreading of tau pathology by binding and reducing unbound N-terminal tau in brain interstitial fluid, thereby delaying the progression of clinical signs and symptoms of PSP. The purpose of this study is to demonstrate the efficacy of BIIB092 in the treatment of PSP and characterize its safety/tolerability profile.

Study Objective(s) and Endpoints:	
The primary objectives of the study are to: 1) Evaluate the efficacy of BIIB092 and 2) Assess the safety and tolerability of BIIB092.
 
The primary endpoints that relate to these objectives are: 1) Change from baseline in the total PSP Rating Scale (PSPRS) score at Week 52 in participants treated with BIIB092 relative to the change in the total PSPRS score in participants treated with placebo and 2) Frequency of deaths, serious adverse events (SAEs), adverse events (AEs) leading to discontinuation, and Grade 3 & 4 laboratory abnormalities.
 
Key secondary objectives and endpoints are as follows:
 
• To evaluate the efficacy of BIIB092, compared to placebo, as measured by a change from baseline in the Movement Disorder

CONFIDENTIAL

The information contained herein may not be used, disclosed, or published without the written consent of Biogen MA Inc.

Society-sponsored revision of the Unified Parkinson's Disease Rating Scale (MDS-UPDRS) Part II at Week 52.

The impact of BIIB092 on the MDS-UPDRS Part II will be evaluated relative to the change from baseline at Week 52 of the BIIB092-treated participants to that of the placebo-treated participants.

- To evaluate the efficacy of BIIB092, compared to placebo, as measured by the Clinical Global Impression of Change (CGI-C) at Week 52.

The impact of BIIB092 on the CGI-C scale score will be evaluated at Week 52 in the BIIB092-treated participants and compared to that of the placebo-treated participants.

- To evaluate the efficacy of BIIB092, compared to placebo, as measured by a change from baseline in the Repeatable Battery for the Assessment of Neuropsychological Disease Severity (RBANS) total score at Week 52.

The impact of BIIB092 on the RBANS scale will be evaluated relative to the change from baseline at Week 52 in the BIIB092-treated participants to that of the placebo-treated participants.

- To assess the impact of BIIB092 on quality of life, relative to placebo, as measured by change from baseline on the Progressive Supranuclear Palsy Quality of Life scale (PSP-QoL) at Week 52.

The impact of BIIB092 on the PSP-QoL scale will be evaluated relative to the change from baseline at Week 52 in the BIIB092-treated participants to that of the placebo-treated participants.

Other secondary objectives and endpoints are as follows:

- To assess the efficacy of BIIB092, relative to placebo, as measured by a change from baseline at Week 48 (Week 52 for Clinical Global Impression of Severity [CGI-S]) on the following instruments:
 - Schwab and England Activities of Daily Living (SEADL) Scale
 - CGI-S
 - Phonemic Fluency Test
 - Letter-Number Sequencing (LNS) Test
 - Color Trails Test
 - Montreal Cognitive Assessment (MoCA)

The impact of BIIB092 on the instruments mentioned above will be evaluated relative to the change from baseline at Week 48 (Week 52

CONFIDENTIAL

The information contained herein may not be used, disclosed, or published without the written consent of Biogen MA Inc.

for CGI-S) in the BIIB092-treated participants to that of the placebo-treated participants.

- To assess the immunogenicity of BIIB092.
Immunogenicity of BIIB092 will be measured by assessment of the presence or absence of anti-BIIB092 antibodies in serum.
- To assess the efficacy of BIIB092, relative to placebo, as measured by absolute and percent change from baseline of brain volumes, as determined by magnetic resonance imaging (MRI), at Week 52 in the following regions:
 - Ventricles
 - Whole brain
 - Midbrain
 - Pons
 - Superior cerebellar peduncle
 - Third ventricle
 - Frontal lobe

The impact of BIIB092 on brain volumes, as determined by MRI in the regions mentioned above, will be evaluated relative to the change from baseline at Week 52 in the BIIB092-treated participants to that of the placebo-treated participants.

Tertiary objectives and endpoints are listed in Section 4.

Extension Objective(s) The primary objective of the open-label extension period is to assess the long-term safety and tolerability of BIIB092 in participants with PSP based on the numbers and percentages of deaths and of participants with SAEs and AEs. The secondary objective is to assess the long-term efficacy of BIIB092 in these participants based on clinical and health-outcomes measures.

Study Design: Randomized, double-blind, placebo-controlled, parallel-group study with an open-label extension period.

This study includes an optional substudy to measure quantitative movement assessments (QMAs) using wearable sensors. The QMAs will measure gait, postural instability, motor function, and falls in a subset of study participants participating in the long-term extension period.

Study Location: Approximately 98 sites are planned globally.

CONFIDENTIAL

The information contained herein may not be used, disclosed, or published without the written consent of Biogen MA Inc.

Number of Planned Participants: Approximately 459 participants will be randomly assigned, in a 2:1 ratio, to receive BIIB092 or placebo (306 participants in the BIIB092 treatment group and 153 in the placebo group).

Anticipating a dropout rate of approximately 25% (based on previous clinical studies in participants with PSP), approximately 345 participants (230 participants in the BIIB092 treatment group and 115 participants in the placebo group) are expected to complete the study through Week 52. Using a two-sided, two-sample t-test, with an alpha level set at 0.05, this sample size will provide 80% power to detect a difference of 3.2 points in the change in PSPRS total score from baseline to Week 52 for BIIB092 relative to placebo, assuming a common standard deviation of 9.95 in the change in PSPRS total score from baseline to Week 52.

Study Population: This study will be conducted in male and female participants with probable or possible PSP.

Women of childbearing potential (WOCBP) and sexually active fertile men with partners who are WOCBP must use highly effective birth control in Study 251PP301.

Detailed criteria are described in Section 6.

Treatment Groups: Study treatment includes both Investigational [Medicinal] Products (IP/IMP) and Non-investigational [Medicinal] Products (Non-IP/Non-IMP) as listed in the following table.

Study Treatment for 251PP301		
Medication	Potency	IP/Non-IP
BIIB092 ^a	50 mg/mL	IP
Placebo ^b (0.9% Sodium Chloride)	N/A	IP

IP = investigational product

[figure not shown]
^a Study treatment supplies may be labeled as BIIB092 or BMS-986168. The two study treatment names refer to an identical study treatment substance.

^b 5% dextrose injection can be used if sodium chloride is not available.

CONFIDENTIAL

The information contained herein may not be used, disclosed, or published without the written consent of Biogen MA Inc.

Study Schematic:

In the 52-week double-blind treatment period of the study, approximately 459 participants in total will be randomly assigned, in a 2:1 ratio, to receive 2000 mg of BIIB092 or placebo (306 participants in the BIIB092 treatment group and 153 in the placebo group) administered by intravenous (IV) infusion approximately once every 4 weeks (Q4W) up to a total of 13 times, with the last dose of the double-blind study treatment administered at Week 48.

At Week 52, participants completing the double-blind treatment period may choose to continue into the open-label extension period of the study. The first dose of 2000 mg of BIIB092 of the open-label extension period will be administered to all participants by intravenous (IV) infusion at Week 52. All participants will be dosed with 2000 mg of BIIB092 by IV infusion approximately once Q4W throughout the duration of the open-label extension period of the study. The duration of participation in the open-label extension period of treatment will vary depending on the date of enrollment of the participant in the study. The open-label extension period is expected to continue until BIIB092 is commercially available, the development program is terminated, or the study is terminated at the discretion of the Sponsor, whichever comes first.

Duration of Treatment and Follow-up:

The study will consist of a 52-week double-blind treatment period followed by an open-label extension period for long-term follow-up.

CONFIDENTIAL

The information contained herein may not be used, disclosed, or published without the written consent of Biogen MA Inc.

2. SCHEDULE OF ACTIVITIES

Table 1: Screening Procedural Outline

Procedure	Screening Visit ^a	Notes
Eligibility Assessments		
Informed Consent	X	Participant is considered enrolled only when a protocol-specific informed consent is signed.
Informed Consent for Caregiver	X	Caregiver is defined as that person who accompanies participant to study visits and has frequent contact with participant of at least 3 hours per week at one time or at different times. Only one caregiver can be designated for participant at a given time. At a minimum, caregiver should personally attend the following study visits: Screening; Baseline; Weeks 12, 24, 36, 48, 52; and Early Discontinuation. Although caregiver assessments cannot be conducted by telephone, caregiver should be available for telephone consultation regarding information on AEs and SAEs when not otherwise attending a scheduled visit.
Inclusion/Exclusion Criteria	X	All inclusion/exclusion criteria should be assessed at screening and confirmed prior to first dose.
Medical History	X	
Concomitant Medications	X	
Mini Mental Status Examination (MMSE)	X	Score ≥ 20 on the MMSE is a criterion for inclusion.
Safety Assessments		
Physical Examination	X	Includes height and weight.
Vital Signs	X	Includes body temperature, respiratory rate, and seated BP and heart rate. BP and heart rate should be measured after the participant has been resting quietly for at least 5 minutes.
Neurological Examination (NE)	X	Besides documenting signs of PSP, the NE should focus on any clinical evidence of increased intracranial pressure (e.g., history of headache, vomiting, or visual disturbances, and neurologic signs such as pupillary abnormalities and papilledema) that might contraindicate a lumbar puncture.

CONFIDENTIAL

The information contained herein may not be used, disclosed, or published without the written consent of Biogen MA Inc.

Procedure	Screening Visit ^a	Notes
12-Lead Electrocardiogram (ECG)	X	ECG should be recorded after the participant has been supine for at least 5 minutes.
Monitor for Serious Adverse Events (SAEs)	X	Following written consent to participate in the study, all SAEs whether related or not related to study treatment that occur during the screening period, continuously throughout the study, and until 30 days following the last dose should be monitored and recorded.
Laboratory Tests	X	Includes blood and urine samples.
Pregnancy Test	X	WOCBP only (serum or urine - local/site).
Follicle-Stimulating Hormone	X	Required for post-menopausal women < 55 (Refer to Appendix 4).
	X	Baseline/Screening Version.
Efficacy Assessments		
Progressive Supranuclear Palsy Rating Scale (PSPRS)	X	
Repeatable Battery for the Assessment of Neuropsychological Disease Severity (RBANS)	X	
Montreal Cognitive Assessment (MoCA)	X	
Phonemic Fluency Test	X	
Letter-Number Sequencing (LNS) Test	X	
Color Trails Test (CTT)	X	Randomization will be stratified by country and screening CTT Part 2 score of either less than or equal to 170 seconds, or greater than 170 seconds.
Magnetic Resonance Imaging (MRI)	X	The MRI should be completed at least 14 days prior to first dose to allow for central assessment of image. A repeat MRI may be requested prior to randomization if protocol standards are not yet met. MRI image quality must be determined to be adequate and local interpretation performed to determine eligibility and to rule out any contraindication to lumbar puncture for participants participating in the [REDACTED]

CONFIDENTIAL

The information contained herein may not be used, disclosed, or published without the written consent of Biogen MA Inc.

Procedure	Screening Visit ^a	Notes
Lumbar Puncture (LP)	X	
██████████
 
The baseline LP may be performed up to Day -1 to allow recovery before dosing. LP should be performed in the morning (between 08:00 and 12:00 hours) to minimize potential diurnal variation of CSF parameters. Any participant with an AE related to LP should not be dosed until the AE has resolved. Use of low dose ASA or other antiplatelet/anticoagulant medications may be associated with a higher risk of LP complications. At the discretion of the Investigator, if not contraindicated, low dose ASA or other antiplatelet/anticoagulant medications may be discontinued for a short period of time prior to performing the LP. Stop and start dates must be documented on the appropriate Concomitant Medication CRF. CSF may be assessed for BIIB092 concentrations, white and red blood cell counts, protein, glucose, levels of unbound N-terminal tau, total tau, phosphorylated tau, and neurofilament light chain (NfL). Participants should be observed for approximately 2 hours after the LP for AEs. LP can be done in either the decubitus or sitting position, however it is preferred that all LPs for each participant are performed in the same position. The position of the participant during the LP will be recorded. LP may be performed under fluoroscopy or with computed tomography guidance at the discretion of the Investigator.

Pharmacokinetic (PK) Assessment		
CSF PK Sampling	X	Collect at time of LP (██████████)
██████████		
██████████	■	██
██████████	■	██████████ ██████████

CONFIDENTIAL

The information contained herein may not be used, disclosed, or published without the written consent of Biogen MA Inc.

Procedure	Screening Visit ^a	Notes
IRT/Clinical Supplies		
IRT	X	Transaction must be made in IRT as follows: For participant number assignment at the time informed consent is obtained. Prior to dosing for study treatment vial assignments (transaction should be made within 1 day prior to dosing).

AE = adverse event; ASA = acetylsalicylic acid; BP = blood pressure; CRF = case report form; CSF = cerebrospinal fluid; CTT = Color Trails Test; ██████████
██████████ ECG = electrocardiogram; IRT = Interactive Response Technology; LNS = Letter-Number Sequencing; LP = lumbar
puncture; MMSE = Mini Mental Status Examination; MoCA = Montreal Cognitive Assessment; MRI = magnetic resonance imaging; NE = neurological
examination; NfL = neurofilament light chain; PK = pharmacokinetic; PSP = Progressive Supranuclear Palsy; PSPRS = Progressive Supranuclear Palsy Rating
Scale; RBANS = Repeatable Battery for the Assessment of Neuropsychological Disease Severity; SAE = serious adverse event; WOCBP = women of
childbearing potential.

^a Screening procedures may be conducted within 42 days prior to first dose unless otherwise specified.

CONFIDENTIAL

The information contained herein may not be used, disclosed, or published without the written consent of Biogen MA Inc.

Table 2: Double-Blind Procedural Outline

Procedure ^a	Week 0 (Day 1)	Weeks 4, 8, 16, 20, 28, 32, 40, 44 ^b (±3 days)	Weeks 12, 24, 36 (±3 days)	Week 48 (±3 days)	Week 52 (±3 days)	Early Discontinuation ^{c, d}	Notes
Eligibility Assessments							
Concomitant Medications	Review of concomitant medication as per Section 7.7.						
Safety Assessments							
Physical Examination	X		X		X	X	Predose.
Targeted Physical Examination	X	X	X	X	X	X	Postdose. Targeted, problem-focused physical examination performed at clinician's discretion (e.g., to evaluate any AEs).
Neurological Examination (NE)	X				X		Besides documenting signs of PSP, the NE should focus on any clinical evidence of increased intracranial pressure (e.g., history of headache, vomiting, or visual disturbances, and neurologic signs such as pupillary abnormalities and papilledema) that might contraindicate a lumbar puncture.
Physical Measurements	X		X		X	X	Weight only.
Vital Signs	X	X	X	X	X	X	Includes body temperature, respiratory rate, and seated BP and heart rate. BP and heart rate should be measured after the participant has been resting quietly for at least 5 minutes.
12-Lead Electrocardiogram (ECG)	X		See notes		X	X	Week 24 only.

CONFIDENTIAL

The information contained herein may not be used, disclosed, or published without the written consent of Biogen MA Inc.

Procedure ^a	Week 0 (Day 1)	Weeks 4, 8, 16, 20, 28, 32, 40, 44 ^b (±3 days)	Weeks 12, 24, 36 (±3 days)	Week 48 (±3 days)	Week 52 (±3 days)	Early Discontinuation ^{c, d}	Notes
Assess Infusion Site	X	X	X	X	X	X	
Laboratory Tests	X	See notes	X	X	X	X	Weeks 4 and 8 only.
Pregnancy Test	X	X	X	X	X	X	For WOCBP only (serum or urine - local/site) within 24 hours prior to dosing.
██████████ ██████████	■	██████████	■	■		■	██████████ ██████████ ██████████
Immunogenicity Assessments							
Serum Anti-BIIB092 Antibody	X	See notes	X	X			Weeks 4 and 8 only. Additional event driven samples may be justified; see Section 14.
Adverse Event Reporting							
Monitor for Non-Serious Adverse Events (NSAEs)	Collection of NSAEs begins at initiation of study treatment and continues throughout the study and until 30 days following the last dose. Participants who discontinue study treatment should have an assessment of AEs 30 days after last dose. ^e						
Monitor for Serious Adverse Events (SAEs)	Following written consent to participate in the study, all SAEs whether related or not related to study treatment that occur during the screening period, continuously throughout the study, and until 30 days following the last dose, should be monitored and recorded. Participants who discontinue study treatment should have an assessment of SAEs 30 days after last dose. ^e						
Efficacy Assessments							
Progressive Supranuclear Palsy Rating Scale (PSPRS)	X		X	X	X	X	
MDS-UPDRS Part II, CGI, RBANS, PSP-QoL	X		X		X	X	
SEADL, Phonemic Fluency, Letter-Number Sequencing, Color Trails Test, MoCA	X		X	X ^f			

CONFIDENTIAL

The information contained herein may not be used, disclosed, or published without the written consent of Biogen MA Inc.

Procedure ^a	Week 0 (Day 1)	Weeks 4, 8, 16, 20, 28, 32, 40, 44 ^b (±3 days)	Weeks 12, 24, 36 (±3 days)	Week 48 (±3 days)	Week 52 (±3 days)	Early Discontinuation ^{c, d}	Notes
[REDACTED]	■		[REDACTED]	■			[REDACTED]
Magnetic Resonance Imaging (MRI)			See notes		X		Week 24 only.
Lumbar Puncture (LP)					X	X	LP should be performed prior to dosing ([REDACTED]).
Pharmacokinetic (PK) Assessments							
Blood PK Sampling	See notes	See notes	See notes	See notes	See notes		Weeks 0, 4, 24, and 48: collect predose and at EOI. Weeks 12, 36, and 52: collect predose only.
CSF PK Sampling					X	X	Collect at the time of LP ([REDACTED]).
Clinical Study Treatment Supplies							
Randomize	X						Prior to dosing for study treatment vial assignments (call should be made within 1 day prior to dosing).
Dispense Study Treatment	X	X	X	X			Duration of infusion will be at least 1 hour.

AE = adverse event; BP = blood pressure; CSF = cerebrospinal fluid; CGI-C = Clinical Global Impression of Change; CGI-S = Clinical Global Impression of Severity; [REDACTED] ECG = electrocardiogram; EOI = end of infusion; [REDACTED]

CONFIDENTIAL

The information contained herein may not be used, disclosed, or published without the written consent of Biogen MA Inc.

Phase 2b Study of BIIB092 in Participants with Progressive Supranuclear Palsy

██████████; LP = lumbar puncture; MDS-UPDRS = Movement Disorder Society-sponsored revision of the Unified Parkinson's Disease Rating Scale; MoCA = Montreal Cognitive Assessment; NSAE = non-serious adverse event; PK = pharmacokinetic; MRI = magnetic resonance imaging; NE = neurological examination; PSP = Progressive Supranuclear Palsy; PSPRS = Progressive Supranuclear Palsy Rating Scale; QoL = quality of life; RBANS = Repeatable Battery for the Assessment of Neuropsychological Disease Severity; ██████████; SAE = serious adverse events; SEADL = Schwab and England Activities of Daily Living scale; ██████████ WOCBP = women of childbearing potential.

- ^a Efficacy assessments requiring participant involvement should be completed prior to dosing with study treatment unless otherwise specified in the notes; specific attention should be paid to conducting the Week 24 MRI within 7 days prior to the Week 24 dosing visit. The study visits at Weeks 0, 12, 24, 36, 48, 52, and Early Discontinuation, which involve the conduct of efficacy assessments, may be completed over a period of up to 3 consecutive days.
- ^b Weeks 28, 32, 40, and 44 may qualify for a home visit if appropriate. See Section 5.1.4 for details.
- ^c Participants who discontinue study treatment during the double-blind period of the study (prior to Week 52) and remain enrolled in the study will be expected to complete scheduled safety and efficacy evaluations at Weeks 12, 24, 36, 48, and 52 until the decision is made to withdraw from the study.
- ^d Early Discontinuation visit procedures should be completed for any participant who discontinues study treatment and also withdraws from the study at any time prior to Week 52. Participants who withdraw from the study should be encouraged to return to the clinic at Week 52 to complete the Week 52 procedures. If the visit cannot be done in person by the participant, the site should attempt a phone call at approximately Week 52 to collect at a minimum vital status (whether the participant is alive or dead) and SAE/AE information on the participant.
- ^e This 30-day assessment of AEs/SAEs may be done by phone if no visit occurs.
- ^f CGI interviews collected from Week 36 will be used to review all areas of the functioning section (including complex daily activities and basic functions) and will be used to determine whether there have been any changes or additions to the functioning at the Week 48 visit, with both the caregiver and participant independently. This will be used to assign the Week 48 SEADL score.

CONFIDENTIAL

The information contained herein may not be used, disclosed, or published without the written consent of Biogen MA Inc.

Table 3: Extension Period Procedural Outline

Procedure	Week 52	Weeks 56, 60, 68, 72, 80, 84, 92, 96, 104, 108, 116, 120, 128, 132, 140, 144, 152, 156, 164, 168, 176, 180, 188, and 192 ^a . (±7 days)	Weeks 64, 88, 112, 136, 160, 184 (±7 days)	Weeks 76, 100, 124, 148, 172, 196 (±7 days)	Early Discontinuation ^b	Notes
Eligibility Assessments						
Concomitant Medications	Review of concomitant medication as per Section 7.7 .					
Safety Assessments						
Physical Examination			See notes	X	X	At Week 64 only.
Targeted Physical Examination		X	X	X	X	Post-dose. Targeted, problem-focused physical examination performed at clinician's discretion (e.g., to evaluate any AEs).
Neurological Examination				See notes		Week 100 only. Besides documenting signs of PSP, the NE should focus on any clinical evidence of increased intracranial pressure (e.g., history of headache, vomiting, or visual disturbances, and neurologic signs such as pupillary abnormalities and papilledema) that might contraindicate a lumbar puncture.
Physical Measurements			X	X	X	Weight only.
Vital Signs		X	X	X	X	

CONFIDENTIAL

The information contained herein may not be used, disclosed, or published without the written consent of Biogen MA Inc.

Procedure	Week 52	Weeks 56, 60, 68, 72, 80, 84, 92, 96, 104, 108, 116, 120, 128, 132, 140, 144, 152, 156, 164, 168, 176, 180, 188, and 192 ^a . (±7 days)	Weeks 64, 88, 112, 136, 160, 184 (±7 days)	Weeks 76, 100, 124, 148, 172, 196 (±7 days)	Early Discontinuation ^b	Notes
12-Lead Electrocardiogram (ECG)				X	X	
Assess Infusion site		X	X	X	X	
Laboratory Tests			See notes	X	X	At Week 64 only.
Pregnancy Test		X	X	X	X	For WOCBP only (serum or urine - local/site).
			■	■	■	
Immunogenicity Assessments						
Serum Anti-BIIB092 Antibody ^c				X		Additional event driven samples may be justified; see Section 14.
Adverse Event Reporting						
Monitor for Non-Serious Adverse Events (NSAEs)	Collection of NSAEs begins at initiation of study treatment and continues throughout the study and until 30 days following the last dose. Participants who discontinue study treatment should have an assessment of AEs 30 days after last dose. ^d					
Monitor for Serious Adverse Events (SAEs)	Following written consent to participate in the study, all SAEs whether related or not related to study treatment that occur during the screening period, continuously throughout the study, and until 30 days following the last dose, should be monitored and recorded. Participants who discontinue study treatment should have an assessment of SAEs 30 days after last dose. ^d					
Efficacy Assessments						
Progressive Supranuclear Palsy Rating Scale (PSPRS)			X	X	X	

CONFIDENTIAL

The information contained herein may not be used, disclosed, or published without the written consent of Biogen MA Inc.

Procedure	Week 52	Weeks 56, 60, 68, 72, 80, 84, 92, 96, 104, 108, 116, 120, 128, 132, 140, 144, 152, 156, 164, 168, 176, 180, 188, and 192 ^a . (±7 days)	Weeks 64, 88, 112, 136, 160, 184 (±7 days)	Weeks 76, 100, 124, 148, 172, 196 (±7 days)	Early Discontinuation ^b	Notes
MDS-UPDRS Part II, CGI, RBANS, PSP-QoL			See notes	X	X	At Week 64 only.
SEADL, Phonemic Fluency, Letter-Number Sequencing (LNS), Color Trails Test (CTT), MoCA				X		
██████████ ██████████				■		██████████
Magnetic resonance imaging (MRI)				See notes		At Week 100 only.
Lumbar Puncture (LP)				See notes		At Week 100 only (██████████ ██████████).
Pharmacokinetic (PK) Assessments						
Blood PK Sampling ^c		See notes		X		At Week 56 only.
CSF PK Sampling ^c				See notes		At Week 100 only (██████████ ██████████).
██████████						
██████████			██████████	■		██████████
██████████				██████████		██████████ ██████████

CONFIDENTIAL

The information contained herein may not be used, disclosed, or published without the written consent of Biogen MA Inc.

Procedure	Week 52	Weeks 56, 60, 68, 72, 80, 84, 92, 96, 104, 108, 116, 120, 128, 132, 140, 144, 152, 156, 164, 168, 176, 180, 188, and 192 ^a . (±7 days)	Weeks 64, 88, 112, 136, 160, 184 (±7 days)	Weeks 76, 100, 124, 148, 172, 196 (±7 days)	Early Discontinuation ^b	Notes
Clinical Drug Supplies						
Dispense Study Treatment	X	X	X	X		Duration of infusion will be at least 1 hour.

AE = adverse event; CGI = Clinical Global Impression; CSF = cerebrospinal fluid; ██████████ CTT = Color Trails Test; ECG = electrocardiogram; ██████████ LNS = Letter-Number Sequencing; LP = lumbar puncture; MDS-UPDRS = Movement Disorder Society-sponsored revision of the Unified Parkinson's Disease Rating Scale; MoCA = Montreal Cognitive Assessment; MRI = magnetic resonance imaging; NE = neurological examination; NSAEs = Non-Serious Adverse Events; PK = pharmacokinetic; QoL = quality of life; PSP = Progressive Supranuclear Palsy; PSPRS = Progressive Supranuclear Palsy Rating Scale; RBANS = Repeatable Battery for the Assessment of Neuropsychological Disease Severity; ██████████ SAEs = serious adverse events; SEADL = Schwab and England Activities of Daily Living scale; ██████████; WOCBP = women of childbearing potential.

^a Weeks 68, 72, 80, 84, 92, 96, 104, 108, 116, 120, 128, 132, 140, 144, 152, 156, 164, 168, 176, 180, 188, and 192 may qualify for home visits if appropriate. See Section 5.1.4 for details.

^b Participants who discontinue study treatment during the open-label extension period of the study (after Week 52) but remain enrolled in the study will be expected to complete scheduled safety and efficacy evaluations at Weeks 64, 76, 88, 100, 112, 124, 136, 148, 160, 172, 184, and 196.

^c Sample to be collected predose.

^d This 30-day assessment of AEs/SAEs may be done by phone if no visit occurs.

CONFIDENTIAL

The information contained herein may not be used, disclosed, or published without the written consent of Biogen MA Inc.

Table 4: Quantitative Assessment Procedural Outline for the Extension Period Substudy

Quantitative Movement Assessments	Substudy Enrollment in the Open-Label Extension Period		
	Baseline Visit ^a	Three-Month Follow-Up Visit ^b	Six-Month Follow-Up Visit ^b
In-Clinic Assessments			
Orthostatic vitals	X		
Visual acuity	X		
Joint-position test	X		
Strength test for hip flexion and knee extension	X		
Sway	X	X	X
Gait	X	X	X
Timed chair stands	X	X	X
Instrumented push and release test	X	X	X
Toe taps	X	X	X
Wrist rotations	X	X	X
In-Home Assessments			
Falls ^c		X	

QMA = quantitative movement assessments

^a The QMA substudy baseline visit will start after participants sign the informed consent form and are eligible to enroll in the substudy.

^b Two follow-up visits will be conducted at 3 and 6 months after the baseline visit of the QMA substudy.

^c Falls will be assessed in-home for 6 months using wearable sensors to capture and quantify falls.

CONFIDENTIAL

The information contained herein may not be used, disclosed, or published without the written consent of Biogen MA Inc.

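### Table 2's Early Discontinuation visit schedules a lumbar puncture without the neurological examination that accompanies every other scheduled puncture

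*Protocol*

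**What the plan says.** All three schedules in Protocol Section 2 give the neurological examination the same two purposes. In Table 1 (Screening) the note reads "Besides documenting signs of PSP, the NE should focus on any clinical evidence of increased intracranial pressure", and it goes on to tie that evidence to a possible contraindication to LP. Table 2 carries the same note, that "the NE should focus on any clinical evidence of increased intracranial pressure", and Table 3 repeats it for a single visit: "Week 100 only. Besides documenting signs of PSP, the NE should focus on any clinical evidence of increased intracranial pressure".

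LP is scheduled as follows.

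- **Table 1:** at Screening, where "The baseline LP may be performed up to Day -1 to allow recovery before dosing".
- **Table 2:** at Week 52 and at Early Discontinuation, with the note "LP should be performed prior to dosing". The CSF pharmacokinetic row carries the same two marks.
- **Table 3:** "At Week 100 only".

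Table 2 marks the neurological examination at Week 0 and Week 52 and nowhere else. Footnote d to Table 2 says who has the extra visit: "Early Discontinuation visit procedures should be completed for any participant who discontinues study treatment and also withdraws from the study", at any time before Week 52. Footnote a says that visits with efficacy assessments, Early Discontinuation among them, "may be completed over a period of up to 3 consecutive days".

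**The concern.** The protocol treats the neurological examination as a look for raised intracranial pressure in connection with LP. If an LP is scheduled at a visit and that examination is not, the site has no prompt to look for the signs the sponsor itself lists (headache, vomiting, visual disturbance, pupillary abnormality, papilledema) before an invasive procedure.

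The visit in question is one where clinical change is plausible. Under Protocol Section 8.1, treatment stops for adverse events or intercurrent illness that make continuing unsuitable, so some participants who go on to withdraw will have changed since baseline. Falls are prominent in PSP (Section 5.6). Subdural hematoma and hydrocephalus are entry exclusions (Section 6.2.1), but either could arise after entry.

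**Working it through.** The check is a cross-tabulation of the schedule, with each row's cells counted against the column headers of its own table.

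| Visit with a scheduled LP | Source | LP | Neurological examination | MRI |
|---|---|---|---|---|
| Screening | Table 1 | yes | yes | yes |
| Week 52 | Table 2 | yes | yes | yes |
| Early Discontinuation, double-blind period | Table 2 | yes | **blank** | blank |
| Week 100 | Table 3 | yes | yes | yes |

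1. **Count.** There are 4 visits with an LP. The neurological examination is also scheduled at 3 of them, so 4 − 3 = 1 is unpaired: Table 2 Early Discontinuation.
2. **Is the LP mark at Early Discontinuation deliberate?** Yes. The CSF pharmacokinetic row is marked at the same two visits and ties the sample to the LP.
3. **Does Table 3 have the same gap?** No. Its Early Discontinuation column has neither an LP nor a neurological examination. The mismatch is confined to Table 2.
4. **Is there a missing LP visit at Week 0?** No. Table 9 lists a predose CSF sample at Week 0, but Table 1 lets the baseline LP run up to the day before dosing, so it is the Screening LP already counted.
5. **Age of the last examination.** In Table 2 the only neurological examination before Week 52 is at Week 0. For a withdrawal before Week 52, the interval from the last scheduled examination to the LP is more than 0 and less than 52 weeks.
6. **Does other text supply the examination?** Sections 5.1.5, 8.2, 8.3 and 9.2 and the footnotes to Table 2 do not add it. Footnote d encourages a return for Week 52 procedures, which include a neurological examination, but that comes after the Early Discontinuation LP.
7. **Does the blank look intended?** Among the legible safety rows of Table 2, those for physical examination, targeted examination, weight, vital signs, ECG, infusion site, laboratory tests and pregnancy test are marked at both Week 52 and Early Discontinuation. The neurological examination is the only legible safety row marked at Week 52 but not at Early Discontinuation, and no visible text gives a reason.

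How many participants are concerned cannot be worked out. The plan expects 459 − 345 = 114 participants not to complete Week 52. How many of them are in the LP subset is redacted, and Section 8.3 exempts those who withdraw consent for any further contact.

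**The case against.** The strongest objection is redaction. Parts of the LP notes in Tables 1 and 2, and other text where LP conduct might be described, are blacked out, and CSF collection details are deferred to manuals that are not available here. An instruction to examine before every LP could sit there. This limits confidence. It does not change the schedule itself: the neurological examination row in Table 2 is fully legible and its Early Discontinuation cell is empty.

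Second, the contrast with the other visits can be overstated. No visit says in so many words that the examination precedes the LP, the three-day allowance covers Week 52 as well, and Week 0 has a neurological examination with no LP. That is fair. Even so, an examination meant to find reasons not to do an LP implies the order, and at the other three visits it is at least scheduled.

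Third, other checks exist. The Early Discontinuation visit includes a physical examination, a targeted examination at the clinician's discretion, adverse event collection and a PSPRS that Section 9.1 assigns to a neurologist. These reduce the practical risk, and a careful clinician may well look anyway. None of them carries the instruction about intracranial pressure.

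Fourth, Table 1 also uses MRI to rule out a contraindication to LP, and Table 2 has a scan at Week 24. A participant who leaves after that scan, if scanned on schedule, has an image less than about 52 − 24 = 28 weeks old, so the 52-week figure applies to the neurological examination alone. But MRI is also blank at Early Discontinuation, which makes this the only LP visit with neither check scheduled. A participant who leaves before Week 24 has no scheduled scan since Screening.

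**Conclusion.** The point holds. Of the four visits in Tables 1 to 3 with a scheduled LP, only Table 2's Early Discontinuation visit omits the neurological examination, and the last scheduled one may be up to just under 52 weeks old. The consequence is for participant safety in the LP subset; the efficacy analyses are untouched. The count is of scheduled visits, not of risk, and the number of participants affected is unknown. The conclusion assumes that the table cells were read in their proper columns, which the cell counts support in all three tables, and that no redacted text or separate manual already requires the examination. The change is worth making because it applies the protocol's own safeguard at very small cost.

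**What to change.** In Table 2, mark the neurological examination at Early Discontinuation for participants having the LP, and add a note that it must be completed before the puncture. The order needs stating because the visit may be spread over three days. The same few words could be added at Week 52, where the same allowance applies.

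The cost is one cell and a short note. The burden is one brief bedside examination, for LP participants only, at a visit they already attend and where a physical examination and a PSPRS are already scheduled.
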